In Phase III, we will build off of the Phase II embedded study with some adjustments to the design to address new research priorities that examine an intervention that is network informed and delivered through community health worker interactions plus digitally-delivered intervention content with the goal of increasing COVID-19 testing and vaccination. This model, if proven effective, can be scaled up to address COVID-19 and other future pandemics. We will utilize the sample of intervention PBGs used in Phase II and will recruit and enroll participants not previously enrolled in either phase I or II from these PBGs using convenience sampling methods. We will use a historical control group consisting of participants from our control arm in Phase II who completed both their baseline and follow-up surveys embedded in the study.

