## Objectives

The primary objective of this study is to:

- 1) Determine the effectiveness of the adapted MC-NET-JITAI (Multilevel Community network-informed Just-In-Time-Adaptive Intervention) versus a historical control group.

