## Study Design:

**RADx-UP Phases I & II.** (The parent studies) We conducted a three-arm group randomized trial to assess the impact of multilevel interventions influencing motivation and access to testing: Arm 1) Community Engaged Just-In-Time Adaptive Intervention (Community JITAI) where we met regularly with community partners and exchanged community-specific information about COVID-19 (testing, infection rates, etc), Arm 2) Standard multilevel intervention (MLI), and a usual practice condition. We randomized 120 PBGs identified as communities with high levels of disparities across our three geographic regions to each condition using a covariate adaptive Randomization (Minimization) Schedule.

The primary outcome for the Phase I and II studies was community-level SARS-CoV-2 testing (primarily PCR testing). This measure was assessed bi-monthly throughout the study. We also conducted an embedded panel study to 1) compare the effectiveness of the CHW-Facilitated Self-Sampling Intervention (FSSI) vs. CHW Testing Navigation Intervention (TNI). In the ongoing study, we also collected social network data on a sub-sample of individuals to explore the influence of social networks on testing decision-making and behavior.

**RADx-UP Phase III:** Our Phase III study design focuses on **vulnerable communities** selected to intervention and control conditions and takes advantage of the fact that these communities were randomized to conditions using methods to ensure balanced arms. In Phase III, we will combine the two intervention conditions (TNI & FSSI), and will receive the MC-NET-JITAI. The study will include PBGs from each of the two intervention conditions in Phase II; they will be matched to the comparison PBGs on variables such as size, vaccination and testing rates, and the disparities index with the control group. The intervention will last 8 weeks; individuals will be recruited and asked to complete a survey (including RADx-UP common data elements).

In Phase III, we will utilize a historical control group consisting of 400 participants from the control arm who completed the baseline and follow-up surveys in the Phase II embedded study.

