**Study Population:**

In the intervention study arm, we will enroll up to 431 individuals and 400 historical control group participants.

**Inclusion/exclusion criteria for intervention study arm.** In this study, the inclusion criteria for the enrolled intervention study arm individuals include being aged 18 years to 89 years and having a smartphone that accepts text messages. The exclusion criteria will include: (1) having been diagnosed with COVID-19 in the past 30 days based on a positive test (antigen or PCR) or a clinical diagnosis, (2) having tested for COVID-19 with PCR or antigen test within the past 30 days, (3) not being available in the recruitment area in the next 60 days, (4) having been an embedded study participant and (5) having been a snowball study participant.

**Selection of the study population.** Three large regions of Texas: 1) Houston/Harris County; 2) Cameron County in South Texas; and 3) seven counties, including the city of Tyler in Northeast Texas. The communities prioritized in this proposal include populations with medical comorbidities, and underserved Hispanics and African Americans in three racially diverse regions: South Texas, Houston/Harris County, and Northeast Texas.

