### Control Arm:

**Control PBGs:** Since we are utilizing a historical control study design, we are not recruiting any new control participants for this Phase III main study. Instead, we will analyze the survey data already collected from the Phase II embedded study control participants.

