- 3) **Missing data:** The enrolled individuals completing the follow-up survey constitute the analysis set. Every effort will be made to keep all participants in the study and to obtain required data at each scheduled time point. All information for patients who dropped out from the study will be recorded and stored in the database. Traditional regression techniques usually assume that all data are complete and will produce unbiased estimates and valid inferences under missing completely at random (MCAR) assumption. We will examine drop-outs, missing data and measurement errors which are common problems with longitudinal data structure to be able to identify accurate missing data mechanisms and patterns so that we can explain missing data mechanism. If the missing data are non-ignorable/informative in the sense that missingness may depend on the missing observations, modeling of the informative missing data or dropout processes will be conducted. An attempt will be made to incorporate the missing values mechanism into the model as discussed in Little and Rubin. All Analyses will be performed primarily using widely available tools in SAS® version 9.4 (SAS Institute, Cary, NC) or R, at a significance level of 0.05.
- 4) **Quality Assurance (QA) & Quality Control (QC) Procedure** Upon completion of resolving data cleaning, the data quality control process will be initiated. The QC process involves 1) randomly selected patients (10-20%), 2) comparing source documents to CRFs, and 3) comparing CRFs with the database. In all processes, we will select critical variables that determine the safety/effectiveness of what will be used in statistical analysis.

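### The historical control group is restricted to follow-up completers with no retention figure, so dropout can be examined and modelled in the intervention arm only

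*Combined protocol and SAP*

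**What the plan says.** The only primary objective is between arms: "Determine the effectiveness of the adapted MC-NET-JITAI" against a historical control group (Objectives).

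The control group is defined by completion. Study Design has "400 participants from the control arm who completed the baseline and follow-up surveys in the Phase II embedded study"; General Information has "participants from our control arm in Phase II who completed both their baseline and follow-up surveys"; the Subject Duration row of the opening summary table says the same. The Control Arm paragraph describes the data source without repeating the condition: "we will analyze the survey data already collected from the Phase II embedded study control participants". Study Population gives the two sizes together: "we will enroll up to 431 individuals and 400 historical control group participants". The 431 are people enrolled at baseline; the 400 are people who finished.

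On missing data (Data Monitoring and Data Management, item 3), the plan says "The enrolled individuals completing the follow-up survey constitute the analysis set", a sentence that appears again in Statistics under the MC-NET-JITAI analysis. The same item says "All information for patients who dropped out from the study will be recorded and stored in the database" and, if missingness is informative, "modeling of the informative missing data or dropout processes will be conducted". It does not say how either applies to the historical controls.

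The Statistics section lists two analyses that use controls: the ratio of odds ratios for intervention versus control, and a GLMM fitted to both cohorts. The sample-size text allows for 45% loss in the intervention cohort. No section states how many people enrolled in the Phase II control arm or what share completed follow-up.

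**The concern.** A ratio of odds ratios cancels dropout bias only if selective retention distorts the paired odds ratio by the same factor in both arms. The protocol gives reasons to doubt that it does. Phase III participants are recruited by convenience sampling, whereas Phase II used systematic sampling with a random start. Phase III participants also receive test kits, up to three text messages a week and contact with community health workers, and the calendar period differs.

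To judge whether retention was similar, one needs to know who left in each arm. The plan keeps that information for the intervention arm and defines it out of the control arm. The promised dropout work can then inform one side only of the comparison that answers the primary objective. A difference in who stays could appear as an intervention effect, or hide one, with nothing in the trial's data to show it.

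**Working it through.** **1. The plan's own figures.** Inputs from the sample-size section: discordance 0.19, OR 2.5, one-sided alpha 2.5%, power 80%, loss 45%.
- No-to-yes share b = 0.19 × 2.5/3.5 = 0.1357. Yes-to-no share c = 0.19/3.5 = 0.0543. Difference 0.0814, the stated 8%.
- Exact McNemar power at N = 237, with discordant pairs Binomial(237, 0.19) and success probability 2.5/3.5, is 0.800.
- 237/(1 − 0.45) = 430.9, so 431. Planned intervention dropouts: 431 − 237 = 194.

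Both figures reproduce. They size a test within the prospective cohort and use no controls.

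**2. How many controls may be unseen.** Phase II control loss is not in the documents. For assumed losses d, enrolment behind 400 completers is 400/(1 − d), rounded up:

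| Assumed loss | Enrolled | Dropouts outside the definition |
|---|---|---|
| 10% | 445 | 45 |
| 20% | 500 | 100 |
| 35% | 616 | 216 |
| 45% | 728 | 328 |

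**3. How selection enters.** In each arm the paired OR is b/c. Selective retention multiplies it by a factor s:
- if retention depends on follow-up testing, s = retention of follow-up testers / retention of non-testers;
- if it depends on baseline testing, s = retention of baseline non-testers / retention of baseline testers.

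So observed ratio of odds ratios = true ratio × s(intervention)/s(control). Equal factors cancel.

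**4. Size under assumed factors.** Assume no true effect, 19% discordance among completers in each arm, and 237 versus 400 completers. The variance of each log OR is 1/(n × 0.19 × OR/(1 + OR)) + 1/(n × 0.19/(1 + OR)), with OR = s. The two variances are summed and the square root is the SE. One-sided rejection is Φ(ln(ratio)/SE − 1.96).

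| s intervention | s control | Ratio | One-sided rejection |
|---|---|---|---|
| 1.5 | 1.5 | 1.00 | 2.5% |
| 1.5 | 1.25 | 1.20 | 6.9% |
| 1.25 | 1 | 1.25 | 8.6% |
| 1.5 | 1 | 1.50 | 18.5% |
| 1 | 1.25 | 0.80 | 0.5% |

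With s = 1.5 in the intervention arm throughout, the ratio is 1.00, 1.20 or 1.50 depending only on the control factor. The last row shows that the bias can also run against the intervention.

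**5. Why correcting one arm is not enough.** Assume that 60% of baseline non-testers and 45% of baseline testers return in the intervention arm. Then s = 0.60/0.45 = 1.33, and a true OR of 2.5 is observed as 3.33. With an assumed 30% testing at baseline, overall retention is 0.7 × 0.60 + 0.3 × 0.45 = 0.555, close to the planned 55%. Weighting that arm by retention given baseline status returns 2.5.
- If s = 1 in controls, the between-arm ratio is then correct.
- If s = 1.33 in controls too, the unweighted ratio was already correct, and weighting the intervention arm alone multiplies it by 1/1.33 = 0.75.

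The dataset as defined cannot tell these two cases apart. That is the specific cost of leaving control dropouts out.

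**The case against.** The strongest reply is that the comparison is symmetric. A reader might infer from 431 beside 400 that intervention dropouts are analysed and control dropouts are not. The analysis-set sentence rules that out: intervention non-completers are kept in the database but not analysed, and the sample-size text already separates 431 enrolled from 237 analysed. This stands. The imbalance is in the information available to assess or correct dropout, not in who is analysed.

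A second reply is that the 1.33 in step 5 is not caused by the control definition. That also stands: it arises in the intervention arm, and if control retention is unselective, weighting the intervention arm alone removes it. It must not be read as an estimate of bias in this trial. What remains is that the assumption about controls cannot be checked.

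Third, the Control Arm paragraph might be read as contradicting the completer definition. It carries no completer condition, but its purpose is to say that no new controls are recruited, and it is compatible with the narrower wording elsewhere.

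Fourth, the intervention arm excludes anyone tested in the past 30 days, and the primary outcome has no stated look-back window. On a 30-day window, baseline testing would hardly vary in that arm. This is a fair limit on the baseline-testing illustration and a reason not to rest the weights on that variable alone.

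**Conclusion.** The concern holds in a limited form. The control group is conditioned on completing follow-up, Phase II control retention is not stated, and the promised dropout examination and modelling can be carried out for the intervention arm only. Differential dropout could therefore bias the ratio of odds ratios and the combined GLMM without being seen.

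Neither the size nor the direction of any such bias can be worked out from the documents. The factors, control losses, 60%/45% retention and 30% baseline testing used above are all assumptions, and the results show range and mechanism only.

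A reader might go further and say that dropout can never be compared or corrected across arms. The documents do not support that. It is true of the dataset as defined, but the controls come from the team's own Phase II study, and retrieving dropouts' baseline records is neither planned nor ruled out. Nor does the point reach the McNemar test: the control definition leaves it and its sizing untouched, although that test alone does not answer the stated objective.

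**What to change.** 1. In the opening summary table, General Information, Study Design and Study Population, define the historical controls as all Phase II control-arm enrollees with a baseline survey. State how many enrolled and how many completed follow-up.
2. Import the control dropouts' baseline records from the Phase II database.
3. Amend the analysis-set sentence in both places (the missing-data item and the MC-NET-JITAI analysis paragraph) so that the between-arm analyses may use baseline records of non-completers in both arms. Without this, the imported records would still be excluded.
4. Keep the completer analysis. Add a ratio of odds ratios with retention weights estimated separately in each arm, using baseline variables collected in both phases.
5. Report retention by arm and by baseline characteristics beside the between-arm result.

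The cost is a data pull, one added analysis, some rewording and slightly wider weighted intervals. No recruitment or sample-size change follows. Baseline weights correct only dropout explained by the measured baseline variables. If dropout depends on follow-up testing itself, the retention table still shows how exposed the comparison is, but the weights do not remove the bias.

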**Random Selection of Intervention Individuals within the PBGs:**

Participants who live in a PBG randomized to the intervention arm will be invited to participate in the trial for that arm. In each of the selected intervention PBGs, individuals will be selected via convenience sampling procedures described below under sample selection.

**Study Population:**

In the intervention study arm, we will enroll up to 431 individuals and 400 historical control group participants.

**Inclusion/exclusion criteria for intervention study arm.** In this study, the inclusion criteria for the enrolled intervention study arm individuals include being aged 18 years to 89 years and having a smartphone that accepts text messages. The exclusion criteria will include: (1) having been diagnosed with COVID-19 in the past 30 days based on a positive test (antigen or PCR) or a clinical diagnosis, (2) having tested for COVID-19 with PCR or antigen test within the past 30 days, (3) not being available in the recruitment area in the next 60 days, (4) having been an embedded study participant and (5) having been a snowball study participant.

**Selection of the study population.** Three large regions of Texas: 1) Houston/Harris County; 2) Cameron County in South Texas; and 3) seven counties, including the city of Tyler in Northeast Texas. The communities prioritized in this proposal include populations with medical comorbidities, and underserved Hispanics and African Americans in three racially diverse regions: South Texas, Houston/Harris County, and Northeast Texas.

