**Primary and Secondary Outcome Measures:**

The pre-post surveys will assess the following behavioral measures:

1. Primary Testing Outcome: COVID-19 antigen testing using individual-level data.
2. Secondary Vaccination Outcome: COVID-19 vaccination uptake using individual-level data.
3. Secondary Outcomes: Mitigation measures if a positive test is obtained including mask wearing, isolating, and notifying close contacts.

**Study Survey:** Project personnel will use the survey platform REDCap (Research Electronic Data Capture) survey software to collect the study survey responses from the participants who consent. The survey instrumentation is designed to capture all relevant demographic characteristics, personal history regarding COVID-19 infection (self, others), testing and vaccination behavior, and psychosocial determinants for testing and vaccination behavior. This survey is composed of all RADx Common Data Elements (CDEs) required by our funder, survey measures taken or adapted from extant COVID-19 health promotion research for our RADx Phase I 2-1-1 survey.

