## Summary of Embedded Study Survey Constructs

Measures / Constructs	Questions	Citation/Tool
Testing behavior	Testing for COVID-19, ever tested, last 30 days, positivity, access to testing	Funder required items, Novel items
COVID-19 history	COVID-19 sickness, hospitalization (self or others)	Funder required items, Novel items
Intention to test	Likelihood of testing (ever, 30 days), intention to test as needed	Funder required items, Novel items
Self-efficacy to test	Certainty of ability to be tested given situational contexts	Adapted self-efficacy measures following Maibach (1995) 
Pandemic safety behaviors	Wearing masks in private settings, wearing masks in public settings, washing/sanitizing hands, intentional social distancing (Never, some of the time, very often, all of the time)	Adapted for CEAL Program from Center for Economic and Social Research Understanding America Study Coronavirus Tracking Survey. https://www.phenxtoolkit.org/covid19/source
Vaccination	Vaccine uptake, type, doses	Funder required items
Trusted Sources of Information	Sources of information (doctor, media, health department, etc)	Funder required items
COVID-19 Perceived Susceptibility/Severity	How concerned are you about contracting COVID-19? How likely is it that you will get COVID-19?	Savoia E. et al, 2021 

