## Statistics

**Statistical Analysis - Main Study Primary Outcomes.** We will conduct a series of analyses regarding the primary outcome variable - testing for COVID-19. First, we will conduct McNemar's test on data from the prospective cohort only. In addition to the test p-value, the odds ratio of COVID-19 testing for post-intervention versus baseline will be evaluated to assess the intervention effect. Second, based on both the prospective cohort and historical controls, we will find inferences for the ratio of odds ratios for intervention versus control. Third, using the prospective cohort, we will build a multi-level generalized linear mixed model (GLMM) including time as a fixed effect factor to evaluate intervention effect. Multiple random effects will be specified to account for the hierarchical structure of persons nested within PBGs nested within regions. Additionally, we will test variables such as individual demographics and baseline measures of rapid testing uses and include significant variables as the fixed effect factors. We will also test the PBG-level of Social Determinants of Health (SDOH) (e.g., % of minority, % of people with no insurance) to investigate the SDOHs as a potential effect modifier on the intervention effectiveness. We will also compute various network measures based on personal networks and organization affiliation patterns associated with COVID-19-related outcomes. Finally, we will build a GLMM to data of both the prospective cohort and historical controls. We will specify proper random effects to account for hierarchical nesting structure.

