### Sample Size for Testing the primary hypothesis in this study.

We have estimated the sample size of the prospective cohort based on the primary hypothesis that individuals experiencing the intervention of Phase III will have higher levels of effective use of SARS-CoV-2 testing than their testing at baseline. The McNemar test, together with the odds ratio (OR) of COVID-19 testing for post-intervention versus baseline, will be used to assess the intervention effect. Preliminary data yielded a discordance of 19% between baseline and follow-up measurements. The ORs were 3.4, 2.3, and 2.3 for Harris, Cameron, and NETX, respectively. The OR for the pooled data was 2.55. We use an OR of 2.5 and a discordance of 19%, which represents an 8% difference in the proportion of testing at follow-up compared to baseline, to size the prospective cohort. For a one-sided test at the significance level of 2.5%, a **sample size of 237 is needed to provide 80% power** for confirming the intervention effect. To allow for a **45% loss to follow-up**, 431 participants need to be enrolled at baseline. The table below provides the size options for a one-sided McNemar test of alpha 2.5% and power 80%.

Proportion of discordance	Odds ratio (OR)	Difference in proportion of testing pertaining to OR	Required sample size	Enrollment allows for a 35% loss to follow-up	Enrollment allows for a 45% loss to follow-up
0.19	2	6%	393	605	715
0.19	2.5	8%	237	365	431
0.19	3	9.5%	177	273	322
0.3	1.5	6%	681	1048	1239
0.3	1.727	8%	387	596	704
0.3	2	10%	249	384	453
0.3	2.75	14%	128	197	233

**Statistical Analysis - MC-NET-JITAI.** We will analyze the secondary outcome measures using the McNemar test, conditional logistic regression model, generalized linear mixed model (GLMM). The enrolled individuals completing the follow-up survey constitute the analysis set. In GLMM, we will specify proper random effects to account for hierarchical nesting structure. Secondary analyses will examine the relation between knowledge, attitudes, and intentions on testing and vaccination decisions and we will use the same multilevel GLMM models.

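### The 30-day testing exclusion can tilt the cohort-only pre-post test towards the intervention, depending on a look-back that the protocol text does not state

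*Combined protocol and SAP*

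**What the plan says.** - **Eligibility.** Under Study Population, exclusion (2) for the intervention arm is "having tested for COVID-19 with PCR or antigen test within the past 30 days". The criteria are given for that arm only. Study Design describes the 400 historical controls only as Phase II control participants who completed both surveys.
- **Outcome.** Primary and Secondary Outcome Measures gives "Primary Testing Outcome: COVID-19 antigen testing using individual-level data", with no time window. The Statistics and sample-size sections word the outcome differently, also without a window. The survey constructs table lists "Testing for COVID-19, ever tested, last 30 days, positivity, access to testing", so its only dated testing items are ever tested and last 30 days.
- **Analysis.** Statistics says "First, we will conduct McNemar's test on data from the prospective cohort only", with the pre-post odds ratio used to assess the intervention effect. A cohort-only mixed model follows, "including time as a fixed effect factor to evaluate intervention effect". Using the historical controls, "we will find inferences for the ratio of odds ratios for intervention versus control", and a combined mixed model is planned last. Objectives names the comparison with historical controls as the primary objective.
- **Sizing.** The primary hypothesis is that "individuals experiencing the intervention of Phase III will have higher levels of effective use of SARS-CoV-2 testing than their testing at baseline". On the inputs: "Preliminary data yielded a discordance of 19% between baseline and follow-up measurements". With an odds ratio of 2.5, this gives 237 completers and 431 enrolled.
- **Timing.** Recruitment allows follow-up from 5 weeks to about 4 months after the initial visit. Part A of the baseline survey may be completed up to 7 days after a first home visit. After event or phone screening, no limit is set.

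**The concern.** Eligibility selects people for not having tested recently, and the sizing analysis then asks whether they test more later. If the outcome window falls mainly inside the 30 days emptied by the exclusion, a return to ordinary testing looks like an intervention effect. The McNemar test takes equal numbers of yes-to-no and no-to-yes changes as its null, and that null would be false before any intervention was delivered.

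The primary hypothesis and the 237/431 sample size rest on this cohort-only test. The control comparison would remove the distortion only if controls were restricted in the same way and asked about the same window, and the documents state neither.

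**Working it through.** **1. The plan's own figure.** Inputs: discordance 0.19, odds ratio 2.5, one-sided 2.5%.
- No-to-yes: 0.19 × 2.5/3.5 = 0.1357, or 32.2 of 237.
- Yes-to-no: 0.19/3.5 = 0.0543, or 12.9 of 237.
- Exact McNemar power at n = 237 is 0.800, and 237/0.55 = 430.9, so 431. The arithmetic reproduces.

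**2. Last-30-days item, baseline all zero, no effect.** Follow-up is at least 35 days after the initial visit, so the follow-up window does not reach back to that visit. All discordant pairs run no-to-yes. The exact test rejects with 6 or more testers (0.5^6 = 0.0156; 0.5^5 = 0.031 is too large). The false-positive chance is P(X ≥ 6), X ~ Binomial(237, q). The documents give no background 30-day rate q, so a range is assumed.

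**3. Gap of D days between screening and survey.** Tests in the gap can make baseline positive: e = 1 − (1 − q)^(D/30). Then no-to-yes = q(1 − e) and yes-to-no = e(1 − q). False-positive chance of the exact test:

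| q | all-zero baseline | D = 7 | D = 14 | D = 21 |
|---|---|---|---|---|
| 1% | 3.3% | 2.0% | 1.2% | 0.7% |
| 2% | 33.8% | 15.6% | 7.0% | 3.1% |
| 3% | 71.7% | 32.6% | 13.1% | 4.9% |
| 5% | 98.0% | 60.2% | 25.1% | 8.1% |

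Each gap column supposes that every participant had that gap. These are illustrations, not bounds.

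**4. Other look-backs W, follow-up at F days, constant testing rate.** Let h = −ln(1 − q)/30. The exclusion leaves W − 30 open days at baseline and W − max(0, min(30, W − F)) at follow-up. Shared open days are S = max(0, W − F − 30). A and B are the open days unique to baseline and to follow-up. Then no-to-yes = exp(−h(A+S))(1 − exp(−hB)) and yes-to-no = (1 − exp(−hA))exp(−h(S+B)). If W ≥ F + 30, both windows contain the same emptied days, A = B, and the exclusion adds no bias. That threshold is 65 days at 5 weeks, 86 at 8 weeks and 150 at 4 months (120 days).

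| W | F | A, B | OR with no effect | rejection at q = 2%, 5%, 10% |
|---|---|---|---|---|
| 60 | 35 | 30, 35 | 1.17–1.18 | 2.0%, 3.7%, 6.1% |
| 60 | 56 | 30, 56 | 1.88–1.96 | 12.9%, 34.6%, 65.5% |
| 90 | 35 or 56 | A = B | 1.00 | at most 1.9% |
| 90 | 120 | 60, 90 | 1.52–1.58 | 11.1%, 28.1%, 50.9% |
| 180, 365 | 35, 56, 120 | A = B | 1.00 | at most 2.0% |

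**5. Do the sizing inputs fit a dated item?** They need about 13 yes-to-no pairs of 237.
- Last 30 days: with D = 7, 237 × e(1 − q) gives 0.55, 1.09, 1.63 and 2.68 pairs at q = 1%, 2%, 3% and 5%.
- Ever tested: a true yes cannot become a no, so reversals come only from recall or reporting error. On this item it is the item itself, not the exclusion, that makes the McNemar null fail.

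**The case against.** The strongest reply is that nothing names the last-30-days item as primary. The sizing inputs argue against it, and Statistics plans to test baseline rapid-test use as a covariate, which presumes that it varies. The constructs table also has an undated entry on testing for COVID-19, and the survey itself, listed as an attachment, may fix the wording. This stands: the bias is conditional, not established. It does not settle the matter, because the protocol text leaves open a listed item on which the first analysis would fail.

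The size is also uncertain. The background rate is assumed, and Background Information says only that self-test use remains low. At 1% testing the inflation is slight or absent. A constant rate over the study period is a simplification.

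The historical-control comparison is already planned, and it is the stated objective. That also stands and makes the remedy cheap. But if Phase II controls did not face the same exclusion, the ratio of odds ratios does not cancel the bias. On the 30-day item, the near-empty yes-to-no cell leaves that ratio barely estimable.

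Two stronger readings are tempting. A reader might infer that the primary test is bound to succeed, but the longer look-backs in step 4 show no exclusion bias. A reader might also infer that the sample size is miscalculated, but it reproduces exactly. The doubt is whether its inputs describe this cohort and this outcome.

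**Conclusion.** The concern holds in conditional form, and the plan needs changing before analysis. On the last-30-days item with an all-zero baseline, the exact test would reject 3% to 98% of the time with no effect as 30-day testing goes from 1% to 5%. With a uniform 7-day gap the range is 2% to 60%. The bias persists for a 60-day look-back at 8 weeks (OR about 1.9). It is absent for 90 days at 5 or 8 weeks, and for 180 days or longer.

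The 19% and 2.5 inputs sit badly with both dated items. The preliminary data therefore probably used another measure or came from people without this exclusion; the documents do not say which. These sizes rest on 237 completers, the exact one-sided 2.5% test, an assumed background rate and constant testing.

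**What to change.** 1. State the primary item and one look-back, the same at baseline, at follow-up and in both groups. Reconcile it with exclusion (2) and the 19%/2.5 inputs, and say whether the preliminary data had that exclusion.
2. Base the effectiveness conclusion on the historical-control comparison already planned. State whether Phase II applied the 30-day exclusion. If not, restrict controls to those with no test in the 30 days before baseline. On the 30-day item, compare follow-up proportions instead of a ratio of pre-post odds ratios, adjusting for time to follow-up.
3. If the chosen look-back is one on which the exclusion empties baseline relative to follow-up, report the cohort-only McNemar test, odds ratio and time model descriptively, not as evidence of the intervention effect.
4. Restate power for the control comparison.

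The cost is SAP wording and a filter on data already collected. The downside is power. For an 8-point difference (two proportions, pooled variance, one-sided 2.5%, before clustering):

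| Control testing | 237 vs 400 | 237 vs 380 (5% of controls removed) | 237 vs 320 (20% removed) |
|---|---|---|---|
| 5% | 93% | 93% | 91% |
| 10% | 81% | 81% | 78% |
| 15% | 71% | 70% | 67% |
| 20% | 64% | 63% | 60% |

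The shares removed are assumptions. The documents give no intraclass correlation; an assumed design effect of 1.25 with 380 controls lowers power to 87%, 72%, 61% and 54%. Differences in calendar time and in sampling (systematic in Phase II, convenience in Phase III) remain and should be stated as limitations.
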